To achieve this aim, we will conduct an online survey with 1,000 PLWHA with HANA conditions, recruited from national social networking websites, to learn about their symptom experience and self-care strategies that they use to mitigate their symptoms. Our study team will incorporate the most frequently reported symptoms and appropriate self-care strategies into our VIP system. The VIP-HANA system, which will provide tailored self-care strategies based on HANA conditions and gender.

Specific Aim 1b: Evaluate the VIP-HANA system for violations of usability principles.

Specific Aim 2: Compare the efficacy of VIP-HANA to a control arm for ameliorating symptom frequency and intensity and secondary health outcomes in 100 PLWHA with HANA conditions over 6 months.

Our hypotheses are that use of VIP-HANA as compared to a control arm will:

- a) Decrease symptom frequency and intensity (primary outcome measures) in the treatment arm as compared to the control arm;
- b) Decrease frailty as measured by Fried’s frailty phenotype;
- c) Improve functional and emotional status, quality of life, and morbidity; and
- d) Improve adherence to antiretroviral therapy (ART).

Specific Aim 3: Understand PLWHA’s perceptions of the predisposing, enabling, and reinforcing factors for VIP-HANA use with theoretically-guided focus group sessions.

We will conduct focus groups, using the PRECEDE-PROCEED model with Aim 2 intervention arm participants, to understand their perceptions related to VIP-HANA use.

DESIGN AND METHODS TABLE

Table 1 presents and overview of the design, participants and data analysis plan

Table 1. Overview of Design, Methods, Participants, and Data Analysis			
Analysis			
Aim	Design/Methods	Participants	Data Analysis
1a	Online Survey	PLWHA with HANA conditions(N=1000) and PLWHA without HANA conditions (N=1000)	Descriptive and thematic analysis of most frequently reported symptoms, symptom attribution, self-care strategies and information source.

1b	Heuristic evaluation, Usability testing (including: cognitive walkthrough, user testing using think-aloud protocol)	Heuristic evaluation: human-computer interaction experts (N=5); User testing: PLWHA (N=20)	Quantitative and qualitative summary of heuristic violations; thematic analysis of think-aloud protocol, quantitative summary of mouse clicks, time, etc.

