Randomization: This will be a single-blinded study, with subjects blinded to study group assignment. Patients will be randomized (1:1) to VIP-HANA or an attention control group. Both groups will receive secure messaging reminders via their smartphone and will also be asked to report their symptoms on their smartphone via a web app every week. Participants in the VIP-HANA (intervention) group will also receive symptom strategies tailored to symptom reporting, HANA condition(s) and gender. Details of the differences between the intervention and control group can be found above in Table 5 (see Section D.1.b).

Data collection: We will have two levels of data collection.

- 1) Participants will report on their symptom frequency and intensity every week on the VIP-HANA app. Participants in both groups will receive reminder messages to report symptoms every week via the revised Sign and Symptom Check-List for HIV delivered via email. If a participant has not completed the checklist in more than 3 weeks, he/she will receive a reminder email or phone call. Intervention arm participants will complete the revised Sign and Symptom Check-List for HIV every week and receive tailored self-care strategies based on their symptom reporting, HANA condition, and gender. Control arm participants will complete the revised Sign and Symptom Check-List for HIV, but will NOT receive strategies.

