- 2) Participants will complete all secondary study-related questionnaires (see outcome measures below) via an electronic survey at baseline, at a 3-month follow-up visit (after 12 weeks), and at the end of the study at a 6-month follow-up visit (week 26). Participants will complete the study questionnaires at our study site. The survey will be housed on Qualtrics software which is a web-based survey program freely available to Columbia University Medical Center employees. Qualtrics provides a secure HIPAA protected environment. Participants will also complete physical measures at all 3 time points. Participants' height, weight, grip strength, and time taken to walk 15 feet will be measured. We will also abstract information from their medical records, such as CD4 counts and viral load, as indicated in the grant submission. In addition all participants will complete demographic information and other related measures including PHQ-2 (Hirshfield et al., 2008; Kroenke, Spitzer, & Williams, 2003), GAD-2 (Kroenke, Spitzer, Williams, Monahan, & Lowe, 2007), HIV stigma (Berger, Ferrans, & Lashley, 2001; Bunn, Solomon, Miller, & Forehand, 2007), health literacy (Weiss et al., 2005), eHealth literacy (Norman & Skinner, 2006), and perceived social support (Brock, Sarason, Sarason, & Pierce, 1996; Kalichman et al., 2006). In response to the reviewers' concern, all participants will complete the social desirability scale (Reynolds, 1982) which will be included in our final analytic model.

Participants will receive \$25 for completion of study questionnaires at baseline, \$35 at the 3-month follow-up visit, and \$40 at the 6-month follow-up visit for completing the assessment tools. Each week that a participant completes a session of the VIP HANA app, they will be given \$5 (26 weeks x \$5/week = \$130). If a participant does not miss more than 5 sessions, they will earn a bonus of \$20. Participants are eligible for up to \$250.

Outcome Measures. Our primary outcome measures, symptom frequency and symptom intensity, will be measured at baseline and every week for 26 weeks. We used the same study-

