Engagement with Health care Provider	Engagement with Health care Provider Scale ([name] et al., 2000)	
		Number of healthcare visits

CD4, Viral Load	Clinical outcomes	Abstraction
ART Adherence	Visual Analogue Scale Self-report (VAS) (Arnsten et al., 2001; Chesney, Ickovics, et al., 2000; De Costa et al., 2010; Walsh, Mandalia, & Gazzard, 2002)	Week 0, 3-month follow-up, 6-month follow--up
Frailty	Fried's Frailty Phenotype (Brothers et al., 2014; Fried et al., 2001); Used in numerous HIV-related studies (Desquilbet et al., 2007; Desquilbet et al., 2009; Piggott et al., 2013)	
System Use	Log Files	Automated

We are paying particular attention to the symptom experience of the study participants over time, the components of the symptom management strategies (e.g. content and frequency of use) through log files, and symptom status as our primary outcome but multiple secondary outcomes are also of interest. Of particular relevance, one of the assumptions of the model is that once symptoms have been successfully addressed then the secondary outcomes should show improvement. Findings from our RCT will inform this hypothesis.

Data Management and Analysis: All survey data will be stored on a secure server. All multivariate analyses will be preceded by standard descriptive statistics to profile participants in each study group and to examine distributions of all outcome variables and to identify outliers. Descriptive statistics (i.e., means, standard deviations, frequencies, and percentages) will be used to examine demographic characteristics of the sample and the frequency and intensity of the symptoms. We will use intention-to-treat principles for the primary outcome analysis.

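### Only participants are blinded: nothing masks whoever takes grip strength and the timed 15-foot walk at follow-up, so the frailty comparison is open to avoidable observer bias

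*Combined protocol and SAP*

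**What the plan says.** All references are to the combined protocol and SAP.

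- **Blinding.** Specific Aim 2, Randomization: "This will be a single-blinded study, with subjects blinded to study group assignment". No other role is named as blinded, and no section mentions a masked or independent assessor.
- **Physical measures.** Specific Aim 2, Data collection, item 2: "Participants will also complete physical measures at all 3 time points", meaning baseline, 3 months and 6 months. The list covers height and weight, and adds that "grip strength, and time taken to walk 15 feet will be measured". It does not say who measures, what that person knows about allocation, or whether instructions are standardised.
- **Role of frailty.** Hypothesis (b) under Specific Aims begins "Decrease frailty as measured by" and names Fried's phenotype. Table 3 lists the same instrument as a secondary outcome.
- **Other outcomes.** For the primary outcomes, "Participants will report on their symptom frequency and intensity every week on the VIP-HANA app". For the questionnaires, "Participants will complete all secondary study-related questionnaires (see outcome measures below) via an electronic survey". In Table 3, adherence to antiretroviral therapy is self-reported, CD4 count and viral load are abstracted, and system use comes from automated logs.

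**The concern.** Grip strength and a timed walk depend partly on the person running the test: how firmly the participant is urged on, and when the watch is started and stopped. If that person knows the arm and expects the app to help, results can drift in one direction in one arm.

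The expectation is written into the plan. Data Management and Analysis anticipates that VIP-HANA will improve symptoms and that frailty, among other secondary outcomes, will then improve. Blinding participants does not shield the measurer. Intervention participants see self-care strategies on their screens and control participants do not, so a passing remark about the app can reveal the arm.

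What is at stake is the credibility of hypothesis (b). Most other results rest on participants' own reports. A frailty result from masked measurers would be one of the few that do not, and part of that advantage is lost if the measurer may know the arm. The plan already addresses reporting bias by putting a social desirability scale in the final model, but has no counterpart for measurements taken at the visit.

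**Working it through.** The plan gives no SD, effect size or power for frailty, so there is no stated figure to reproduce. The check has two parts.

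**1. Where could an observer influence an outcome?**

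| Outcome | Source in the plan | Room for observer influence |
|---|---|---|
| Symptom frequency and intensity (primary) | Weekly self-report in the app | Little |
| Quality of life, provider engagement | Self-completed electronic survey | Little |
| Adherence | Self-report scale | Little |
| CD4 count, viral load | Abstracted from medical records | Little |
| System use | Log files | None apparent |
| Grip strength, 15-foot walk | Measured at the study visit | Yes: encouragement and timing |

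Two of the three measurement occasions fall at follow-up. The sample-size text plans for 100 participants and 80 completers at 6 months. If everyone is seen at 3 months, the exposed sets number at most about 100 + 80 = 180.

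**2. How much could a shift matter? (illustration)**

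Inputs from the plan: 40 completers per arm; two-sided alpha of 0.05. Assumptions, not in the plan: a continuous frailty measure compared by a simple two-mean z-test, no true effect, and an observer shift of b SD between the arms.

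Standard error in SD units: se = √(2/40) = 0.2236.

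False-positive rate = Φ(b/se − 1.96) + Φ(−b/se − 1.96).

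| b (SD) | b/se | First term | Second term | False-positive rate |
|---|---|---|---|---|
| 0 | 0 | 0.0250 | 0.0250 | 5.0% |
| 0.1 | 0.447 | 0.0652 | 0.0080 | 7.3% |
| 0.2 | 0.894 | 0.1433 | 0.0022 | 14.6% |
| 0.3 | 1.342 | 0.2682 | 0.0005 | 26.9% |

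At 50 per arm (no attrition) the rates for b = 0.1, 0.2 and 0.3 are 7.9%, 17.0% and 32.3%.

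For scale, the difference detectable with 80% power at 40 per arm is (1.96 + 0.842) × 0.2236 = 0.63 SD. A shift of 0.2 to 0.3 SD would be 0.2/0.63 = 32% to 0.3/0.63 = 48% of that. Neither intention-to-treat analysis nor the planned mixed models would remove a shift that runs along the arm.

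**The case against.** The best reply is that the plan is silent on assessors rather than wrong about them. A reader might infer that the measurers are definitely unmasked. The text does not go that far: a single-blind label naming only subjects makes it likely, but neither the measurer's identity nor their knowledge is stated. That stands, so the point is put as staff who may know the arm. Even that staff take the measures is an inference from on-site visits and passive wording.

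A reader might also infer that one small team screens, phones and measures. The documents do not support this. Pre-screening is by study staff, but no caller is named in "If a participant has not completed the checklist in more than 3 weeks, he/she will receive a reminder email or phone call", and neither team size nor overlap of roles is given. The reminder rule applies to both arms and is not shown to affect the measurements.

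The link to frailty is only partly documented. The plan names the phenotype and lists grip and walk time, but does not say that they are its components or give cut-offs. A claim that participants would be reclassified as frail or not frail therefore cannot be supported here. Nor can a claim that bias would exceed the true effect, since neither size is known.

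Finally, frailty is one of several secondary outcomes and carries no power claim. That is correct and limits the consequence. It does not remove the point: frailty is a named hypothesis, and applying the blinding rule as written leaves it unprotected when a simple safeguard is available.

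**Conclusion.** The concern holds in conditional form. The plan blinds only subjects and provides no masking for whoever measures grip strength and walk time at 3 and 6 months. These measures appear to feed hypothesis (b), so that comparison is open to avoidable observer bias.

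The size of the bias is unknown. The range of about 7% to 27% depends wholly on the assumed shift of 0.1 to 0.3 SD and on a simple two-mean comparison; it shows sensitivity and is not an estimate. The conclusion also assumes that staff take the measures and that these enter the frailty phenotype. Both are reasonable readings, but neither is spelled out.

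The primary outcomes are self-reported and unaffected. This is a change the trial should make, not one on which its main conclusion depends.

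**What to change.** Amend the Randomization and Data collection paragraphs of Specific Aim 2 to state that, at the 3- and 6-month visits and using existing staff:

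- the person who measures grip strength and walk time has no access to the allocation, wherever it is held;
- the measures are taken at the start of the visit, before any discussion of the app;
- a fixed instruction and encouragement script is followed;
- participants are asked not to mention app content to the measurer.

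If existing staffing does not allow masking at some visits, keep the visit order and the script, record which measurements were unmasked, and report them as such.

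The cost is a short amendment, a script, some control of access to the allocation, and minor scheduling. The visit order and script need no extra staff. Whether masking can be covered at every visit cannot be judged from the documents, which do not describe staffing; hence the fallback. Sample size, alpha and the visit schedule stay as they are.
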